7.3.3 Further endpoint analyses

All further endpoints will be considered exploratory in nature.

The analysis of further endpoints over 52 weeks will be performed with the same models and procedures as described for the secondary endpoints in [Section 7.3.2](#).

Further time to event endpoints over the whole trial will be analysed in a descriptive manner. Frequency tables and Kaplan-Meier plots will be produced.

7.3.4 Safety analyses

The primary assessment of benefit-risk of nintedanib in patients with PF-ILD will be based on efficacy and safety data over 52 weeks (using data from Part A of the trial). All safety assessments described below will focus on data collected within the first 52 weeks of the study. In addition, selected safety analyses will be repeated to include data collected beyond 52 weeks (during Part B of the trial); further details will be specified in the TSAP.

Adverse events will be coded using the Medical Dictionary for Regulatory Activities (MedDRA) coding dictionary. Standard BI summary tables and listings will be produced. All treated patients will be included in the safety analysis for the overall population and the safety analysis will be repeated for the co-primary population of patients with HRCT with UIP-like fibrotic pattern only. In general, safety analyses will be descriptive in nature and will be based on BI standards. No hypothesis testing is planned.

Kaplan-Meier plots will be produced for the time to premature treatment discontinuation, for the time to first dose reduction and for the time to first treatment interruption.

Statistical analysis and reporting of adverse events will concentrate on treatment-emergent adverse events. To this end, all adverse events occurring between start of treatment and end of the residual effect period will be considered 'treatment-emergent'. The residual effect period is defined as the 28 days after the date of the last dose of trial medication. Adverse events that start before first drug intake and deteriorate under treatment will also be considered 'treatment-emergent'. Based on the half-life of the study drug, the medical residual effect period is 7 days after the last dose of trial medication. Therefore, additional analysis of safety data will be made for adverse events that occur between the start of treatment and up to 7 days after the date of the last dose of trial medication will be analysed in addition.

Frequency, severity, and causal relationship of adverse events will be tabulated by system organ class and preferred term after coding according to the current version of MedDRA.

Summary tables will be produced for the adjudication results of MACE and deaths.

Laboratory data will be analysed both quantitatively as well as qualitatively. The latter will be done via comparison of laboratory data to their reference ranges. Values outside the reference range as well as values defined as clinically relevant will be highlighted in the listings. Treatment groups will be compared descriptively with regard to distribution parameters as well as with regard to frequency and percentage of patients with abnormal values or clinically relevant abnormal values.

Vital signs, physical examinations, or other safety-relevant data observed at screening, baseline, during the course of the treatment and at the end-of-treatment evaluation will be assessed with regard to possible changes compared to findings before start of treatment.

7.3.5 Pharmacokinetic analyses

Pre-dose plasma concentrations (C_{pre,ss}) of nintedanib will be tabulated with descriptive statistics in the CTR. For pharmacokinetic analysis and displays, concentrations will be used in the same format as reported in the bio-analytical report. Only concentrations within the validated concentration range will be used and these will be reported using actual sampling times.

7.4 INTERIM ANALYSES

No interim analysis is planned but the conduct of the trial will be monitored by a DMC until the primary analysis is performed. The purpose, scope and tasks of the DMC are described in [Section 3.1.1](#).

The primary assessment of benefit-risk of nintedanib in patients with PF-ILD will be based on efficacy and safety data over 52 weeks. The primary analysis will therefore be performed once the last patient reaches the Week 52 Visit (Part A: Visit 9).

7.5 HANDLING OF MISSING DATA

7.5.1 Efficacy Endpoints

The effect of missing data on the primary endpoint will be investigated using multiple imputation techniques.

For the primary endpoint, for each co-primary analysis population, the following subsets of patients will be defined:

1. Patients with an FVC result at week 52 who received trial medication until week 52.
2. Patients with an FVC result at week 52 who prematurely discontinued trial medication prior to week 52.
3. Patients without an FVC result at week 52 who were alive at week 52.
4. Patients without an FVC result at week 52 who died prior to week 52.

These four subsets of patients will be used in sensitivity analyses to estimate the treatment effect under differing assumptions around the persistence of efficacy after withdrawal of trial medication. [Table 7.5.1: 1](#) describes the planned sensitivity analyses for handling missing primary endpoint data. Sensitivity analyses 1 and 2 will only be performed if there are at least 10 patients included in patient subset 2 in each treatment group.

Table 7.5.1: 1

Sensitivity analyses for handling missing primary endpoint data

Analysis	Patient subset 3: No FVC result but alive at Week 52		Patient subset 4: No FVC result and died prior to Week 52	
	Handling of missing FVC result	Underlying assumption	Handling of missing FVC result	Underlying assumption
Primary analysis	Missing data handled by model.	Assumes missing at random. Discontinued patients would have behaved similarly to patients who did not discontinue.	Missing data handled by model.	Assumes missing at random. Discontinued patients would have behaved similarly to patients who did not discontinue.
Sensitivity analysis 1	Based on the slope estimates for drug and placebo in patient subset 2.	Patients without a result would have behaved similarly to discontinued patients with a result who are in the same treatment group.	Based on the slope estimates for placebo patients in patient subset 2, but truncated so that those who died are more severe.	Patients who died before week 52 would have behaved in a similar or worse way to a placebo patient who prematurely discontinued.
Sensitivity analysis 2	Based on the slope estimates for placebo in patient subset 2.	Patients without a result would have behaved similarly to discontinued placebo patients with a result.		
Sensitivity analysis 3	Based on the slope estimates for placebo in patient subsets 1 and 2.	Patients without a result would have behaved similarly to placebo patients with a result regardless of whether they prematurely discontinued treatment or not.	Based on slope estimates for placebo patients in subsets 1 and 2, but truncated so those who died are more severe.	Patients who died before week 52 would have behaved in a similar or worse way to a placebo patient regardless of whether they prematurely discontinued treatment or not.

Further sensitivity analyses will be described in detail in the TSAP.

In the analysis of all other continuous endpoints, missing data will not be imputed. The mixed effect model will handle missing data based on a likelihood method under the "missing at random assumption".

In the analysis of time-to-event endpoints, missing or incomplete data will be handled using standard survival analysis techniques (i.e. censoring). Efficacy time-to-event endpoints will be calculated from the randomization date.

In the analyses of the categorical endpoints, missing data will be imputed using the worst case.

7.5.2 Safety

Missing or incomplete AE dates will be imputed according to BI standards. Other missing safety data will not be imputed.

7.5.3 Plasma concentrations

Descriptive statistics of concentrations at specific time points will be calculated only when at least 2/3 of the individuals have concentrations within the validated concentration range. The overall sample size to decide whether the "2/3 rule" is fulfilled will be based on the total number of samples intended to be drawn for that time point (i.e. BLQ, NOR, NOS, and NOA are included).

7.6 RANDOMIZATION

Within each randomization HRCT pattern stratum ("UIP-like fibrotic pattern only" or "Other fibrotic patterns"), patients will be randomized in blocks to double-blind treatment in a 1:1 ratio. Approximately equal numbers of patients will be randomized to each treatment group. The randomization system will include caps for the two HRCT pattern strata so that approximately two thirds of the patients are randomized to the "UIP-like fibrotic pattern only" stratum and one third is randomized to the "Other fibrotic patterns" stratum (i.e. approximately 400 and 200 patients to each stratum, respectively). As a consequence of these caps randomization might be put on hold in one stratum temporarily and may mean that screened patients cannot be randomized immediately.

The Sponsor will arrange for the randomization and the packaging and labelling of trial medication. The randomization list will be generated using a validated system, which involves a pseudo-random number generator so that the resulting treatment will be both reproducible and non-predictable. The block size will be documented in the CTR. Access to the codes will be controlled and documented.

7.7 DETERMINATION OF SAMPLE SIZE

Lack of published data from randomized clinical trials in patients with PF-ILD leads to uncertainty both on the rate of forced vital capacity (FVC) decline and on its variability in the planned study population.

The main assumption of the study is that patients with PF-ILD, independent from their original ILD classification, at some point in time, exhibit a progressive fibrosing phenotype. In this group of patients with PF-ILD, the disease behaviour over time (e.g. lung function, mortality) appears to follow a course similar to IPF, a typical example of PF-ILD.

Based on the existing literature for IPF, the observed mean values for the annual rate of decline in FVC or the FVC change from baseline to 45–52 weeks in patients treated with placebo was approximately between 140 mL and 250 mL (see [Section 10.5](#)).

The currently available data in different ILDs show that the ILD injury pattern, in particular the presence of UIP, is associated with worse prognosis ([P11-07084](#), [R10-6539](#), [R16-0554](#), [R15-3264](#), [R16-1567](#), [R14-3529](#), [R16-0752](#), [R16-1568](#)). Based on this, the study will be enriched for patients with UIP pattern. UIP pattern will be defined based on HRCT using the same HRCT criteria as in the Phase III IPF trials for nintedanib ([P15-04977](#), [P15-05695](#)) and described in [Section 1.1](#). Since these criteria differ slightly from the current definition of radiologic UIP provided in the ATS/ERS guidelines (P11-07084), patients with screening HRCT meeting the protocol criteria for UIP will be referred to as “patients with HRCT with UIP-like fibrotic pattern only”. Patients with HRCT patterns not meeting the protocol criteria for UIP will be referred to as “patients with other HRCT fibrotic patterns”.

For scenario planning for the sample size calculation, a rate of decline of 150-200 mL/year has been assumed for PF-ILD patients with HRCT with UIP-like fibrotic pattern only. For the patients with other HRCT fibrotic patterns, the FVC rate of decline is assumed to be slightly lower than in PF-ILD patients with HRCT with UIP-like fibrotic pattern only: between 120 and 150 mL/year.

Nintedanib is hypothesized to have the same relative effect on all patients with PF-ILD (an approximate 50% reduction in the annual rate of decline in FVC). However it is expected that the absolute effect difference between groups will be the largest in the patients with HRCT with UIP-like fibrotic pattern only since these patients are assumed to have a larger annual rate of decline than patients with other HRCT fibrotic patterns.

The treatment effect to detect is therefore in the range of 75-100 mL/year for the PF-ILD patients with HRCT with UIP-like fibrotic pattern only and of 60-75 mL/year in the PF-ILD patients with other HRCT fibrotic patterns.

Given some expected heterogeneity in the rate of decline across the PF-ILD subpopulations, the variability is assumed to be larger than in IPF for patients with other HRCT fibrotic patterns with a standard deviation (SD) of 400 mL/year. For patients with HRCT with UIP-like fibrotic pattern only, a more homogeneous group of patients, the variability is assumed to be the same as observed in IPF with a SD of 300 mL/year.

By enrichment, it is planned to recruit 400 PF-ILD patients with HRCT with UIP-like fibrotic pattern only, making up two thirds (66.7%) of the study population. This design will be used in order to maintain a high power to detect a clinically meaningful effect of nintedanib in the rare disease of PF-ILD.

There will be two co-primary analysis populations: the first will comprise all patients (the overall population); the second will comprise all patients with HRCT with UIP-like fibrotic pattern only. Since establishing an effect in either of these two populations is considered clinically relevant, the trial will be considered positive if it establishes efficacy in either one of the two populations or in both.

In order to maintain an overall type 1 error rate of 5%, a Hochberg procedure will be used ([R97-1003](#)). This multiplicity adjustment strongly controls the overall Type I error rate in clinical trials with a targeted subpopulation ([R16-1041](#)). For the primary endpoint, statistical significance will be declared if the analyses in both co-primary populations are significant at the two-sided 5% level, **or** if the analyses in either co-primary population are statistically significant at the two-sided 2.5% level. Given the proposed design properties it is calculated that applying this procedure, the overall alpha spent will be 4.35% so the overall Type I error control is below 5%. This is based upon the summation of the probabilities of rejecting H_0 under various combinations of results for the co-primary populations within the Hochberg procedure (calculated using SAS® Version 9.4, see [Appendix 10.6](#) for details).

[Table 7.7: 1](#) below presents the power properties of this study for several scenarios for the treatment effect in the two co-primary populations.

Table 7.7: 1: Power properties for several scenarios for the treatment effect in the two co-primary populations

	Patients with HRCT with UIP- like fibrotic pattern only Co-primary	Patients with other HRCT fibrotic patterns	Overall patient population Co-primary	
Scenario 1				
Assumed treatment difference in absolute change in FVC in mL/year (SD)	100 (300)	75 (400)	92 (337)	
Individual test power	90.2%		90.3%	
Overall Power [*]				92.6%
Scenario 2				
Assumed treatment difference in absolute change in FVC in mL/year (SD)	75 (300)	60 (400)	70 (337)	
Individual test power	67.2%		68.2%	
Overall Power [*]				72.4%
Scenario 3				
Assumed treatment difference in absolute change in FVC in mL/year (SD)	75 (300)	75 (400)	75 (337)	
Individual test power	68.2%		73.4%	
Overall Power [*]				75.8%

FVC, forced vital capacity; SD, standard deviation.

Power calculations are based on Hochberg procedure at the overall type 1 error rate of 5% (two-sided), with 200 patients with HRCT with UIP-like fibrotic pattern only and 100 patients with other HRCT fibrotic patterns per treatment group.

*The overall power is the probability of concluding statistical significance for either of the co-primary populations.

Power calculated using SAS[®] Version 9.4 (see [Appendix 10.6](#) for details)

Drop-out is not accounted for in the sample size calculation since all patients from the treated set are expected to have sufficient data to be included in the primary analysis.

With a sample size of 300 patients randomized per treatment group, and 600 patients in total including 400 patients with HRCT with UIP-like fibrotic pattern only and using a Hochberg procedure, there will be:

- more than 90% power to detect a treatment effect of 100 mL/year assuming a standard deviation of 300 mL/year in the patients with HRCT with UIP-like fibrotic pattern only ,
- more than 90% power to detect a treatment effect of 92mL/year assuming a standard deviation of 337 mL/year in the overall population, and

- more than 90% overall power (probability to conclude significance for the overall population or for the patients with HRCT with UIP-like fibrotic pattern only)

In fact with this sample size and study design, even in the scenario assuming the lowest rate of FVC declines for the patients with HRCT with UIP-like fibrotic pattern only and for the patients with other HRCT fibrotic patterns (scenario 2), there will be almost 80% overall power to detect an effect of nintedanib.

The proposed sample size will therefore provide adequate power to demonstrate a clinically important treatment benefit on the primary endpoint even in scenarios where the annual rate of decline in both PF-ILD co-primary patient populations is much lower than observed for IPF patients in the Phase III IPF trials.

In general, no key secondary endpoints are planned for the trial since there is no data in the published ILD literature on which to base assumptions for treatment effect and power for the proposed main secondary endpoints. However, the endpoints defined as main secondary are those which are considered most relevant to the assessment of the effect of nintedanib in PF-ILD. These endpoints will provide the main supportive evidence to the primary endpoint assessment.

The mortality rate in PF-ILD is anticipated to be similar to IPF ([R15-3264](#), [R16-0554](#)). Power calculations based on the mortality rate expected and later observed in the IPF trials with nintedanib indicated that for demonstrating a statistically significant treatment benefit for nintedanib in all-cause mortality approximately 6,000 patients would be required for a placebo-controlled trial of 52-week duration in IPF ([P14-06844](#)). The current study in PF-ILD is powered for the primary endpoint, annual rate of decline in FVC with a total sample size of 600 patients. The study is therefore not powered to demonstrate a statistically significant reduction in mortality over 52 weeks. However, all-cause mortality as a main secondary endpoint will provide further clinically meaningful information on the effect of nintedanib in PF-ILD.

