3. DESCRIPTION OF DESIGN AND TRIAL POPULATION

3.1 OVERALL TRIAL DESIGN AND PLAN

This is a multi-centre, multi-national, prospective, randomized, placebo-controlled, double blind clinical trial to investigate the efficacy and safety of nintedanib at a dose of 150 mg bid, in patients with PF-ILD over 52 weeks.

A total of approximately 600 patients will be randomized, 300 in the active treatment arm and 300 in the placebo group. The study population will be enriched for patients with HRCT with UIP-like fibrotic pattern only applying the criteria used in the Phase III IPF studies for nintedanib, and as determined by the central reviewers (see [Section 3.3.4](#)). It is planned to enrol 400 patients with PF-ILD with HRCT with UIP-like fibrotic pattern only, i.e. two thirds (66.7%) of the randomized patients and 200 patients with PF-ILD with other HRCT fibrotic patterns.

After signing informed consent (IC), the initial screening visit (Visit 1) will be performed to determine eligibility. Following completion of Visit 1, patients with established PF-ILD, as assessed by the Investigator, will enter a screening period of maximum 12 weeks to confirm HRCT eligibility and determine HRCT pattern for randomization (see Section 3.3.4), and to allow for wash-out of treatment for ILD, if applicable (see [Section 4.2.2](#)).

Written confirmation by the central readers that the protocol criteria for qualifying HRCT are met will be mandatory for randomization. For detailed procedural assessments of patient's eligibility, please refer to the [Flowchart Part A](#) and [Section 6.2.1](#).

Once HRCT eligibility is confirmed, Visit 2 will be scheduled to collect all clinical and safety information, and review all inclusion and exclusion criteria. Patients will be randomized in 1:1 ratio to either nintedanib or placebo and then enter the treatment phase for a minimum of 52 weeks. Randomization (stratified by HRCT pattern: "UIP-like fibrotic pattern only", or "Other fibrotic patterns") will be performed by phone or Internet, using an Interactive phone/web Response System (IRT).

Part A of the study will consist of Visits 2 through 9, which will occur within one year of randomization. Following completion of the week 52 visit (Visit 9), patients will continue to have study visits every 16 weeks (Part B) until the end of the trial. Intermediate laboratory tests for safety monitoring will be performed as needed for additional safety monitoring until the end of the trial.

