10.6 SAS CODE FOR SAMPLE SIZE CALCULATION

```
%MACRO PRBHOCH(a,b,d1,d2,SD1,SD2,f,n,dat);
*****;
** a = 1-sided Type 1 error used in powering **;
** b = Type II error used in powering **;
** d1 = hypothesized overall treatment effect **;
** d2 = hypothesized subpopulation treatment effect **;
** SD1 = assumed SD overall **;
** SD2 = assumed SD subpopulation **;
** f = fraction in subpopulation **;
** n = Planned sample size per treatment group **;
** dat = dataset name **;
*****;

DATA x;
a=&a;
b=&b;
f=&f;
d1=&d1;
SD1=&SD1;
d2=&d2;
SD2=&SD2;
n=&n;
ns=round(f*n,1);
r=sqrt(f); ** correlation between subpopulation and overall population test statistics **;

** under null using Hochberg**;
zhoc1= probit(1-0.025);
zhoc2= probit(1-0.025/2);

** critical values for Hochberg**;
choc1025= zhoc1*SD1*sqrt(2/n);
choc10125= zhoc2*SD1*sqrt(2/n);
choc2025= zhoc1*SD2*sqrt(2/ns);
choc20125= zhoc2*SD2*sqrt(2/ns);

**under alternative Hochberg**;
t1025=(choc1025-d1)/(SD1*sqrt(2/n));
t10125=(choc10125-d1)/(SD1*sqrt(2/n));
t2025=(choc2025-d2)/(SD2*sqrt(2/ns));
t20125=(choc20125-d2)/(SD2*sqrt(2/ns));

** Hochberg overall type 1 error**;
phoc1025= PROBBNRM(-zhoc1,50000,r);
phoc10125= PROBBNRM(-zhoc2,50000,r);
```

```
phoc2025= PROBBNRM(-zhoc1,50000,r);  
phoc20125= PROBBNRM(-zhoc2,50000,r);  
phoc1025nphoc2025= PROBBNRM(-zhoc1,-zhoc1,r);  
phoc10125nphoc2025= PROBBNRM(-zhoc2,-zhoc1,r);  
phoc20125nphoc1025= PROBBNRM(-zhoc1,-zhoc2,r);  
pp1 = phoc10125 - phoc10125nphoc2025;  
pp2 = phoc20125 - phoc20125nphoc1025;  
phoc1sig = phoc1025nphoc2025 + pp1;  
phoc2sig = phoc1025nphoc2025 + pp2;  
HocTy1 = phoc1sig + phoc2sig - phoc1025nphoc2025; * 1-sided Type 1 error;
```

```
** Hochberg overall power **;  
xhoc1025= PROBBNRM(-t1025,50000,r);  
xhoc10125= PROBBNRM(-t10125,50000,r);  
xhoc2025= PROBBNRM(-t2025,50000,r);  
xhoc20125= PROBBNRM(-t20125,50000,r);  
xhoc1025nkhoc2025= PROBBNRM(-t1025,-t2025,r);  
xhoc10125nkhoc2025= PROBBNRM(-t10125,-t2025,r);  
xhoc20125nkhoc1025= PROBBNRM(-t20125,-t1025,r);  
xx1 = xhoc10125 - xhoc10125nkhoc2025;  
xx2 = xhoc20125 - xhoc20125nkhoc1025;  
xhoc1sig = xhoc1025nkhoc2025 + xx1; * Power for overall population test;  
xhoc2sig = xhoc1025nkhoc2025 + xx2; * Power for sub-population test;  
HocPow = (xhoc1sig + xhoc2sig - xhoc1025nkhoc2025); * Overall power;
```

```
run;
```

```
PROC PRINT;  
RUN;
```

```
data &dat;set x;  
Dat="&dat";  
run;  
  
%MEND;
```

```
%prbdoch(0.025,0.10,92,100,337,300,0.667,300 ,d1);  

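### The sample size text claims almost 80% overall power in scenario 2, but the protocol's own table and code give 72.4%, and the code's correlation ignores the unequal SDs

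*Protocol*

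**What the plan says.** Protocol section 7.7 plans 300 patients per arm, "with 200 patients with HRCT with UIP-like fibrotic pattern only and 100 patients with other HRCT fibrotic patterns per treatment group". For the UIP-like stratum "the variability is assumed to be the same as observed in IPF with a SD of 300 mL/year"; for the other patterns it assumes 400 mL/year, which pools to 337 mL/year overall.

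Significance is declared if both co-primary populations reach two-sided 5%, or "if the analyses in either co-primary population are statistically significant at the two-sided 2.5% level". The footnote to Table 7.7: 1 confirms the basis: "Power calculations are based on Hochberg procedure at the overall type 1 error rate of 5% (two-sided").

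For scenario 2 (75 mL/year UIP-like, 60 other, 70 overall) the table gives individual powers of 67.2% (UIP-like) and 68.2% (overall), and an overall power of 72.4%. The text after the table names the same scenario, sample size and design and says "there will be almost 80% overall power to detect an effect of nintedanib". The following sentence concludes from this that power is adequate even when decline is much lower than in the IPF trials.

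On type I error, section 7.7 states that "the overall alpha spent will be 4.35% so the overall Type I error control is below 5" per cent. The calculation is in Appendix 10.6, where the macro defines "r=sqrt(f); correlation between subpopulation and overall population test statistics".

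**The concern.** Two statements about one scenario disagree by more than 7 points, and rounding cannot account for that. Scenario 3, which is more favourable, reaches only 75.8% in the table, so the text claims more for the worst case than the table gives for a better one.

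The figure also carries weight. Section 7.7 opens by admitting uncertainty about both the rate of decline and its variability in this population, so the low-decline scenario is the relevant robustness check on 600 patients. Section 7.7 makes no allowance for drop-out. An ethics committee or regulator reading the text would accept the sample size on a figure the protocol does not support. SAP section 3 sends its readers to the protocol for sample size, so nothing later corrects it.

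Separately, the macro's correlation omits the SD ratio although the protocol assumes different SDs in the two strata. The stated alpha and all three overall powers depend on that correlation.

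**Working it through.** **Inputs** (section 7.7, Appendix 10.6): n = 300 per arm, of whom 200 UIP-like; f = 0.667; overall SD1 = 337; UIP-like SD2 = 300. Effects (overall, UIP-like) are 92 and 100, 70 and 75, 75 and 75 mL/year. Section 3.1 gives the allocation: "Patients will be randomized in 1:1 ratio to either nintedanib or placebo". Critical values: z = 1.960 (two-sided 5%) and 2.241 (two-sided 2.5%).

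Pooled SD check: sqrt(2/3 × 300² + 1/3 × 400²) = 336.65, which rounds to the stated 337.

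**Step 1. Reproduce the plan with r = sqrt(0.667) = 0.8167.**

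Standard errors: overall 337 × sqrt(2/300) = 27.52; UIP-like 300 × sqrt(2/200) = 30.00.

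Scenario 2 expected statistics: 70/27.52 = 2.544 and 75/30.00 = 2.500.

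Overall power = P(both > 1.960) + P(overall > 2.241, UIP-like < 1.960) + P(UIP-like > 2.241, overall < 1.960) = 0.6295 + 0.0525 + 0.0421 = 0.7241.

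Individual powers: 0.6295 + 0.0525 = 68.2% overall; 0.6295 + 0.0421 = 67.2% UIP-like (exact sum 0.67159).

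Alpha = 2 × (0.01151 + 2 × 0.00511) = 4.35%.

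Scenarios 1 and 3 give 92.6% and 75.8%. Every tabled figure and the stated alpha reproduce. The text figure does not.

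**Step 2. Look for a route to almost 80%.**

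| Scenario 2 calculation | Power |
|---|---|
| Hochberg, as coded | 72.4% |
| Overall population alone at 5% | 72.0% |
| UIP-like population alone at 5% | 70.5% |
| Hochberg, correlation corrected (step 3) | 74.3% |
| Hochberg, inverse-variance-weighted overall test | 74.0% |
| Either population at unadjusted 5%, r = 0.817 | 79.6% |

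Only the last comes close. It drops the multiplicity adjustment and has a family-wise error of 7.7% (8.2% at r = 0.727). The documents do not say whether the text figure came from there.

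**Step 3. Correlation under the protocol's SDs.**

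The overall difference is D_all = f × D_sub + (1 − f) × D_other, with independent strata, so Cov(D_all, D_sub) = f × Var(D_sub).

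With Var(D_sub) = 2 × SD2²/(f × n) and Var(D_all) = 2 × SD1²/n,

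r = f × sqrt(Var(D_sub)/Var(D_all)) = sqrt(f) × SD2/SD1 = 0.8167 × 300/337 = 0.727.

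Re-running step 1 with r = 0.727:

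| Quantity | Stated | Corrected |
|---|---|---|
| Overall alpha | 4.35% | 4.52% |
| Overall power, scenario 1 | 92.6% | 93.5% |
| Overall power, scenario 2 | 72.4% | 74.3% |
| Overall power, scenario 3 | 75.8% | 77.6% |

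For scenario 2 the terms are 0.6107 + 0.0717 + 0.0602 = 0.7425 (rounded terms add to 0.7426). Individual powers move by at most 0.3 points in any scenario. A simulation of 4 million trials per scenario gave r = 0.727 to 0.728, alpha 4.5%, and powers of 93.5%, 74.3% and 77.6%.

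**Step 4. What 80% in scenario 2 would take.**

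| Change from scenario 2 | r = 0.817 | r = 0.727 |
|---|---|---|
| UIP-like effect, both strata scaled together | 82.1 mL/year | 80.4 mL/year |
| UIP-like effect, other patterns held at 60 | 83.3 mL/year | 81.3 mL/year |
| Patients per arm, effects unchanged | 360 | 345 |

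**The case against.** The correct 72.4% is in the table just before the faulty sentence, so it is not hidden. The three bulleted claims of more than 90% power all refer to scenario 1 and all hold (90.2%, 90.3%, 92.6%); scenario 2 is an added robustness remark. No analysis uses the figure: the decision rule is the fixed 5% and 2.5% Hochberg rule, which needs neither a power nor a correlation. Correcting the text cannot change an estimate or a test.

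The correlation error is also mild. It understates overall power by 0.9 to 1.9 points, alpha remains below 5%, and a two-sample formula is in any case an approximation to the planned random-slope model. Whether 72% to 74% is adequate in a deliberately pessimistic scenario is a matter of judgement, since the protocol sets no threshold.

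All of this stands as a limit on the consequences. It does not remove the contradiction. The adequacy sentence is drawn as an inference from the 80% figure, and a reader of the text alone is given the wrong risk of failure. The two errors work in opposite directions on scenario 2, but correcting the correlation recovers only about 2 of the nearly 8 missing points.

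**Conclusion.** The concern holds, in two parts of different weight.

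The main part is the text claim for scenario 2. It is wrong by about 7.6 points against the table and the code, and by about 5.7 points after the correlation is corrected. The probability of missing the assumed effect is 26% to 28%. The conclusion about adequate power at low decline rates needs rewording.

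The lesser part is the correlation. The stated alpha and overall powers do not follow from the protocol's own SDs, but the shifts are small: 0.17 points on alpha, and power slightly understated. Control of the family-wise error at 5% is unaffected.

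The corrected r assumes the pooled overall estimator implied by an SD of 337 with 300 per arm, the planned two-to-one split of strata, and no loss of data. An inverse-variance-weighted overall estimate has a different correlation (0.883) but leaves scenario 2 at 74.0%.

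**What to change.** In section 7.7, replace the scenario 2 text figure with 72.4%, or with 74.3% if the correlation is corrected in the same edit. Limit the adequacy sentence to what the table supports: above 90% overall power in scenario 1, and roughly 72% to 78% in scenarios 2 and 3.

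In Appendix 10.6, change the line defining r to `r = sqrt(f)*SD2/SD1`. Re-run the macro, then restate alpha as 4.52%, overall power as 93.5%, 74.3% and 77.6%, and the individual powers where they move in the first decimal.

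The cost is a few sentences and one line of SAS. Two stated figures become less favourable (the 80% claim, and alpha by 0.17 points), while the three tabled overall powers rise slightly. The sample size, decision rule and planned analyses do not change.
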